TPVOE ¹¹⁾	
Non-Responders of VOE-CR are subjects who meet any of the following criteria:
 
• Has ≥ 1 adjudicated VOE between 6 months and 18 months after drug product infusion. If a subject has an adjudicated VOE that occurs before 183 days but ends after 183 days after drug product infusion, the subject is considered as a non-responder.• Has any death related to VOE (adjudicated by independent committee) or drug product/study procedure (assessed by investigator) on or before 18 months post-drug product infusion. 
Subjects in the TPVOE who don't meet any of the non-responder criteria above will be excluded from the analysis if they discontinued from the study on or before reaching 18 months post-drug product infusion.
 
If there is no death or discontinuation on or before 18 months post-drug product infusion, the results will be the same as for the primary analysis of VOE-CR, so this supplementary analysis will not be performed in this case.

¹¹⁾ If an interim analysis is performed, subjects should also have or would have at least 18 months of follow up post-drug product infusion.

Analysis for Groups A and B

The number and percentage of subjects achieving VOE-CR will be reported by group for Groups A and B subjects in TPVOE at final analysis, or in TPVOE who have or would have 18 months follow-up at interim analysis. No 95% CI will be presented given the relatively small sample size.

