4.4.3. Analysis of Other Efficacy Endpoints

4.4.3.1. Characterization of Globin Response (only for Group C subjects who have achieved Globin Response)

- Proportion of subjects who meet the definition of Globin Response at Month 24**
 - The numerator is the number of subjects who continuously meet Globin Response criteria from the first date of Globin Response initiating (t_0) to Month 24 visit of HPLC assessment
 - The denominator is the number of subjects who have achieved Globin Response.

If after achieving Globin Response, a subject discontinues from the study before having the Month 24 visit of HPLC assessment, then the subject will also be considered as a non-responder.

The percentage of subjects who maintain Globin Response at Month 24 will be presented with a 2-sided 95% CI using Clopper-Pearson method.

Supplementary Analyses

The following Supplementary analyses will be conducted:

Analysis Population	Supplementary Analysis
TP	
The primary analysis will be repeated, but after achieving Globin Response, subjects with death or discontinuation unrelated to the drug product will be considered as not evaluable.
 
If after achieving Globin Response but before having the Month 24 visit of HPLC assessment, there is death or discontinuation related to the drug product, then the subject will be considered as a non-responder.

- Duration of Globin Response**

Duration of Globin Response is from the first date of Globin Response initiating (t_0) to the date of last HPLC assessment such that the weighted average of HbA^{T87Q} percentage of non-transfused total Hb, non-transfused total Hb, and non-transfused total Hb increase from the baseline total Hb (if baseline total Hb is available) continuously meet Globin Response criteria

during this time period. Duration of Globin Response (in months) and these weighted average values during Globin Response will be summarized.

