5.2. Changes from Previous SAP (Version 2.0)

Section Number	Section	Changes
4.4.1	Analysis of Primary Efficacy Endpoint	
Clarified that only the supplementary analyses for Group C subjects based on the protocol VOEs and the investigator VOEs in TPVOE will be performed for the final CSR.
 
Removed the supplementary analysis in the ITT population with ≥ 4 protocol VOEs in the 24 months prior to Informed Consent. The analysis was performed for the interim CSR, in case the agency wanted the analysis based on the ITT population. The result was however not of the agency's interest. Moreover, this analysis was heavily weighted by subjects who discontinued prior to receiving the benefit of treatment.

4.4.2.1	Adjudicated sVOE-CR	
Clarified that only the supplementary analysis for Group C subjects based on the protocol sVOEs in TPVOE will be performed for the final CSR.
 
Removed the supplementary analysis in the ITT population with ≥ 4 protocol VOEs in the 24 months prior to Informed Consent. See the change above made in Section 4.4.1 for the rationale.

4.4.2.2	Globin Response	Removed the imputation rules of missing HPLC assessments due to COVID-19 pandemic. The imputation rules were never implemented, because of no such cases in data by the end of the pandemic.

Section Number	Section	Changes
		Removed the supplementary analysis in the ITT population with ≥ 4 protocol VOEs in the 24 months prior to Informed Consent. See the change above made in Section 4.4.1 for the rationale.
4.4.3.1	Characterization of Globin Response	Added a supplementary analysis. In the definition, added “After achieving Globin Response, subjects with death or discontinuation unrelated to the drug product will be considered as not evaluable.” This is to exclude the subject who discontinued due to sudden death which was unrelated to the drug product, according to communication with the agency.
4.4.3.2	Hematologic Endpoints	Removed “starting from Month 1 post-drug product infusion”.
4.4.4	Analysis of Exploratory Efficacy Endpoints	Added the analyses of bone marrow smear.
4.4.5	Analysis of Correlation	Added the correlation between HbAT87Q vs. HbS (% of non-transfused total Hb) at Month 6
4.5	Pharmacodynamic Analysis and Correlation Analysis	Deleted the spaghetti plots of PB %LVV+ and AUC of sickled RBCs, and the correlation analyses related to the two parameters.
4.6.1	Adverse Events	Added AE/SAE attributed to SCD post Month 6

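### Read literally, the supplementary analysis of Globin Response at Month 24 drops a responder with an already documented loss who later leaves for an unrelated reason

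*SAP*

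**What the plan says.** The main analysis in SAP 4.4.3.1 has three parts.

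- Numerator: "The numerator is the number of subjects who continuously meet Globin Response criteria from the first date of Globin Response initiating" (t0), through to the Month 24 HPLC assessment.
- Denominator: "The denominator is the number of subjects who have achieved Globin Response".
- Leavers: "If after achieving Globin Response, a subject discontinues from the study before having the Month 24 visit of HPLC assessment", that subject also counts as a non-responder, whatever the cause.

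The supplementary analysis in the same section repeats this analysis with a changed rule for leavers. For unrelated events, "after achieving Globin Response, subjects with death or discontinuation unrelated to the drug product will be considered as not evaluable". For related events the rule is failure, with a time limit: "If after achieving Globin Response but before having the Month 24 visit of HPLC assessment, there is death or discontinuation related to the drug product", the subject is a non-responder. The unrelated-event sentence has no such time limit.

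The change log in SAP 5.2 gives the reason for adding the analysis, after communication with the agency: "This is to exclude the subject who discontinued due to sudden death which was unrelated to the drug product".

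The supplementary analyses of VOE-CR (SAP 4.4.1) and sVOE-CR (SAP 4.4.2.1) treat leavers in another order. They list the failure criteria first and then say: "Subjects in the TPVOE who don't meet any of the non-responder criteria above will be excluded from the analysis" if they left on or before 18 months.

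**The concern.** HPLC is scheduled at Months 1, 2, 3, 4.5 and 6 and then every 3 months to Month 24 (SAP 4.4.2.2), so a loss of response can be on record well before a subject leaves. Because the numerator requires unbroken response from t0, that record already settles the Month 24 outcome as failure. Nothing about that outcome is unknown, and not evaluable is the wrong label for it.

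The supplementary rule asks only two things: was Globin Response achieved, and was the later death or discontinuation unrelated to drug product? It does not ask whether the response was still present. A programmer following the sentence as written would remove the documented failure. Such a subject was never in the numerator, so only the denominator shrinks, and the rate moves up. The result would be presented as the maintenance rate free of unrelated departures, when it might also be free of some real losses.

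**Working it through.** **Is there a plan figure to reproduce?** Neither document gives a figure for the Month 24 proportion. The nearest is the design of the parent endpoint in SAP 3.1: success at 24 of 41, null 40%, alternative 70%, power about 96%. The exact binomial gives power 0.9586 and one-sided alpha 0.0126, and a cutoff of 23 would give alpha 0.0270. The stated figure therefore reproduces, but it does not bear on the rule examined here.

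**Side by side: a responder with documented loss who then leaves for an unrelated reason**

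| Analysis | Order of rules | Result |
|---|---|---|
| Main Month 24 (4.4.3.1) | Continuity required; every early leaver fails | Non-responder |
| Supplementary Month 24, literal (4.4.3.1) | Unrelated leaver removed; no check for earlier loss | Not evaluable |

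The corresponding case in the VOE-CR and sVOE-CR supplementary analyses is a subject with a qualifying event who then leaves. Failure is applied first there, and the subject stays a non-responder.

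**Size, on assumed counts.** Let D be the number of responders, u the unrelated leavers before Month 24, and l those among them with documented loss. All other responders keep the response.

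- Main rate = (D − u)/D
- Literal supplementary rate = (D − u)/(D − u)
- Failure-first supplementary rate = (D − u)/(D − u + l)

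The documents do not give D. The values used are 24 (the success count for 41 subjects), 29 (0.70 × 41 = 28.7, rounded) and 36 (all Group C subjects infused, SAP Table 1, hence the maximum). Intervals are two-sided 95% Clopper-Pearson, as SAP 4.4.3.1 specifies for this proportion.

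One leaver, with documented loss (u = 1, l = 1):

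| D | Literal | Failure first | Rise in rate | Rise in lower limit |
|---|---|---|---|---|
| 24 | 23/23 = 100% (85.2–100) | 23/24 = 95.8% (78.9–99.9) | 4.2 points | 6.3 points |
| 29 | 28/28 = 100% (87.7–100) | 28/29 = 96.6% (82.2–99.9) | 3.4 points | 5.5 points |
| 36 | 35/35 = 100% (90.0–100) | 35/36 = 97.2% (85.5–99.9) | 2.8 points | 4.5 points |

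Three leavers, two with documented loss (u = 3, l = 2):

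| D | Main | Literal | Failure first |
|---|---|---|---|
| 24 | 21/24 = 87.5% | 21/21 = 100% | 21/23 = 91.3% |
| 29 | 26/29 = 89.7% | 26/26 = 100% | 26/28 = 92.9% |
| 36 | 33/36 = 91.7% | 33/33 = 100% | 33/35 = 94.3% |

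One leaver with response intact (u = 1, l = 0): both supplementary rules give the same result, for example 23/23 when D = 24.

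**Direction.** With x subjects maintaining response among n, dropping one documented loss changes x/n to x/(n − 1), a rise of x/[n(n − 1)], which is positive whenever x > 0. For example, 27/30 = 90.0% becomes 27/29 = 93.1%; the numerator stays at 27.

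**The case against.** The strongest reply is textual. The supplementary row says it repeats the primary analysis with a change, and both of its sentences concern only subjects who die or leave. The main analysis has two routes to failure: breaking continuity, and leaving early. The row can be read as replacing only the second, so that a documented loss remains a failure. That reading is open. It is not stated, though, and the VOE-CR and sVOE-CR rows do state the order. What stands is that the defect lies in the literal wording, and a reader who infers that the SAP definitely intends to discard observed losses goes further than the text allows.

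A reader might also infer that such a subject exists and that a reported rate has been inflated. The documents do not support this. SAP 5.2 mentions one subject, with an unrelated sudden death, and does not say that this subject had lost response. All the counts above are assumptions.

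Finally, the consequence is small. Protocol 7.4.4.3 has the secondary endpoints summarised descriptively, and no test or success criterion attaches to this rate. The main analysis counts every early leaver as a failure and will be reported alongside. Duration of Globin Response is summarised, and efficacy data are listed, so a loss would not be hidden. All of this stands and limits the point to a clarification.

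**Conclusion.** The point holds as a wording defect with a narrow reach. Taken literally, the rule is wider than its stated purpose and wider than its counterparts in the same SAP. Relative to counting documented losses as failures, dropping them can only raise the supplementary rate. With 24 to 36 responders and every other responder maintaining response, one dropped loss is worth about 3 to 4 percentage points on the rate and about 4 to 6 on the lower confidence limit. If no responder lost response before an unrelated departure, the effect is nil. The main Month 24 result, the key secondary test of Globin Response and the primary endpoint are untouched.

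**What to change.** Replace the unrelated-event sentence in the supplementary analysis of SAP 4.4.3.1 with:

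> Subjects with death or discontinuation unrelated to drug product before the Month 24 HPLC assessment are not evaluable only if they continuously met the Globin Response criteria (including the no-transfusion condition of Section 4.4.2.2) from t0 through their last HPLC assessment before the event; subjects with a documented loss of response before the event remain non-responders.

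The condition has to cover the whole period from t0. A check of the last HPLC assessment alone would excuse a subject who failed earlier and then met the criteria again, which the numerator definition does not allow. The Month 24 limit brings the sentence into line with the related-event rule.

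The cost is one sentence and one derivation condition. Duration of Globin Response already identifies the last HPLC date through which the criteria were continuously met; if that date is earlier than the subject's last HPLC date before the event, a loss is documented. The stated aim of setting aside the sudden-death subject is still met, provided that subject's response was intact. The downside is that the supplementary rate may be slightly less favourable.

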7.4.4.3. Analyses of Other Secondary Efficacy Endpoints

Analyses of the following secondary efficacy endpoints will be descriptively summarized. More details can be found in the SAP.

Clinical and Disease Evaluation Endpoints:

(Only for subjects with at least 4 VOEs in the 24 months prior to Informed Consent):

- Change in the annualized number of VOEs in the 24 months after drug product infusion compared to the 24 months prior to Informed Consent.

(Only for Group C subjects with at least 4 VOEs in the 24 months prior to Informed Consent):

- Change in the annualized number of severe VOEs in the 24 months after drug product infusion compared to the 24 months prior to Informed Consent.
- VOE-CR24, defined as complete resolution of VOEs between 6 months and 24 months after drug product infusion
- sVOE-CR24, defined as complete resolution of severe VOEs between 6 months and 24 months after drug product infusion

- sVOE-75, defined as at least a 75% reduction in annualized severe VOEs in the 24 months after drug product infusion compared to the 24 months prior to Informed Consent

Note: The analyses regarding severe VOEs will be based on Group C subjects who have at least 4 VOEs in the 24 months prior to Informed Consent.

Characterization of Globin Response (only for Group C subjects who have achieved Globin Response):

- Proportion of subjects who meet the definition of Globin Response at Month 24
- Duration of Globin Response

Hematologic Endpoints:

- Weighted average for the following at Month 6, 12, 18, and 24:
 - non-transfused total Hb
 - HbS percentage of non-transfused total Hb
 - HbS percentage of non-transfused total Hb $\leq 70\%$, $\leq 60\%$, $\leq 50\%$
 - HbA^{T87Q} percentage of non-transfused total Hb
 - non-HbS percentage of non-transfused total Hb
- Assessment of the following over time:
 - non-transfused total Hb
 - HbS percentage of non-transfused total Hb
 - HbA^{T87Q} percentage of non-transfused total Hb
 - non-HbS percentage of non-transfused total Hb
- Change from baseline in hemolysis markers, including absolute reticulocyte count, % reticulocytes/erythrocytes, total bilirubin, haptoglobin, and lactate dehydrogenase
- Change from baseline in markers of iron stores including ferritin, liver iron content, and if assessed at baseline, cardiac iron content
- Change from baseline in annualized frequency and volume of packed red blood cell (pRBC) transfusions between 6 months and 24 months after drug product infusion

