For continuous variables, descriptive statistics such as the number of observations or subjects, mean, standard deviation (SD), median, 25% percentile (Q1) and 75% percentile (Q3) as needed, minimum and maximum values will be presented. Mean, median, Q1, Q3, and 95% confidence intervals (CI) will be rounded to 1 additional decimal place compared to the original data (maximum of 3 decimal places). The SD will be rounded to 2 additional decimal places compared to the original data. Minimum and maximum will be displayed with the same accuracy as the original data. The maximal decimals for SD will be 4.

For categorical variables, summary of the number and percentage within each category of the parameter will be presented. A shift table, for change from baseline, can be provided as appropriate. In the shift table, baseline, the worst value within each visit window post-drug product infusion (if there is more than 1 value), and the worst value during the entire follow-up post-drug product infusion will be presented as needed.

Descriptive summary statistics, as well as 2-sided 95% CI, will be presented on selected parameters, as described in the sections below. The exact CI for proportion will be calculated using Clopper-Pearson exact method.

Longitudinal data (collected serially over time on study) will be presented by appropriate time intervals, such as monthly, quarterly, and so forth, depending on the nature of the data.

For purposes of calculations, a month will be defined as 365.25/12 (30.4375) days and a year as 365.25 days. For reporting by month, calculations will be rounded to the nearest day (i.e., the calculated value at 18 months, 547.9, would be rounded to 548 days; the calculated value at 6 months, 182.6, would be rounded to 183 days).

By-subject listings of data for all completed and discontinued subjects, including screen failures (as appropriate), will be provided. All data listings that contain an evaluation date will contain a relative study day (Rel Day). Pre- and post- drug product infusion study days are numbered relative to the day of drug product infusion, which is designated as Day 1.

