3.13. Final Analysis

A final analysis will be performed when last subject has completed the Month 24 Visit as specified in the protocol or discontinued from the study.

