4.4.2.2. Globin Response

Analysis for Group C

The key secondary efficacy endpoint, Globin Response, defined as meeting the following criteria for a continuous period of at least 6 months after drug product infusion (starting ≥ 60 days after last pRBC transfusion):

- a. Weighted average HbA^{T87Q} percentage of non-transfused total Hb $\geq 30\%$
AND
- b. Weighted average non-transfused total Hb increase of ≥ 3 g/dL compared to baseline total Hb, OR weighted average non-transfused total Hb ≥ 10 g/dL

The detailed definition of Globin Response can be found in [Section 1.2.6.2](#). The analysis population can be found in [Table 4](#).

The weighted average HbA^{T87Q} percentage of non-transfused total Hb is defined as

$$[(t_1 - t_0) \times \frac{(p_0 + p_1)}{2} + (t_2 - t_1) \times \frac{(p_1 + p_2)}{2} + \dots + (t_k - t_{k-1}) \times \frac{(p_{k-1} + p_k)}{2}] / (t_k - t_0)$$

Where

- t_0 represents the time of the first HbA^{T87Q} assessment post-drug product infusion and there is no pRBC transfusion in the previous 60 days, and t_1, t_2, \dots, t_k represent continuous time points for HbA^{T87Q} assessments after t_0 and no pRBC transfusion occurs between these timepoints.
- $p_0, p_1, p_2, \dots, p_k$ represent the HbA^{T87Q} percentage to non-transfused total Hb at each of these time points
- $t_k - t_0$ must be at least 6 months, which is 183 days ([with exception below](#)).

This calculation is invariant to the metric used for the time points, e.g., calendar dates or days from drug product infusion, since the consecutive differences in times would always be measured in number of days.

After drug product infusion, HbA^{T87Q} will be assessed at Month 1, 2, 3, 4.5, 6, and then every 3 months through Month 24. In the situation where there are three consecutive scheduled HbA^{T87Q} assessments in a 6-month period of time (i.e., every 3-month) and scheduled Hb^{AT87Q} assessments are within visit window but are less than 6 months apart, then the ≥ 6 months requirement will not be needed, however, the requirement of starting ≥ 60 days after the last pRBC transfusion still needs to be met. Scheduled visits for assessments are defined in [Appendix 6.2, Table 12](#). The weighted average may be considered as an average AUC calculation for HbA^{T87Q} percentage. Note that the weighted non-transfused total Hb can be calculated in a similar way.

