4.6.6. Overall Survival

Overall Survival (OS) is defined as time from date of drug product infusion (Day 1) to date of death. Overall survival will be censored at the date of last follow-up if subject is alive. If there is any death due to any reason occurring during the study, OS rate at 12 months and 24 months by Kaplan-Meier method will be reported.

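### Duration of Globin Response has no censoring rule, so for subjects still responding at their last HPLC sample the planned summary reports follow-up time from t0

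*SAP*

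**What the plan says.** The definition in SAP 4.4.3.1 begins: "Duration of Globin Response is from the first date of Globin Response initiating (t_0) to the date of last HPLC assessment such that" the weighted averages continuously meet the response criteria over that period. The endpoint sits under the heading "Characterization of Globin Response (only for Group C subjects who have achieved Globin Response"), so only Group C responders enter it. The planned output is one sentence: "Duration of Globin Response (in months) and these weighted average values during Globin Response will be summarized".

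The type of summary comes from SAP 3.2: "For continuous variables, descriptive statistics such as the number of observations or subjects, mean, standard deviation (SD), median", plus minimum and maximum. Protocol 7.4.4.3 adds only this: "Analyses of the following secondary efficacy endpoints will be descriptively summarized". Follow-up ends at Month 24 (SAP 3.13: "A final analysis will be performed when last subject has completed the Month 24 Visit").

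The SAP specifies right-censoring with Kaplan-Meier for one endpoint, overall survival (SAP 4.6.6): "Overall survival will be censored at the date of last follow-up if subject is alive". SAP 3.2 also cuts off continuous data after a hematologic malignancy, but that rule truncates data and does not mark a response as ongoing. SAP 3.12 lists endpoints with special inclusion rules at interim analyses and does not name duration among them.

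**The concern.** A duration has a known end only if the response was seen to fail. A subject still responding at the last HPLC sample has a duration of at least the recorded value. A mean or median that takes such values as complete mainly reflects when t0 fell and how long the subject was followed.

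Two things follow. First, the reported duration rises with later data cuts even when the treatment effect is unchanged. Second, a responder who dies or withdraws for unrelated reasons enters as a completed short duration although no loss was observed. The change table in SAP 5.2 suggests this is not hypothetical: it explains the supplementary analysis of the Month 24 proportion by a sudden death judged unrelated to drug product. Duration was given no matching rule. For a one-time gene therapy, readers will take this endpoint as evidence of durability.

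**Working it through.** **The plan's own figures.** The documents give no expected value or power for duration. The nearest stated figure is the power for Globin Response, whose responders form this population: N = 41, null 40%, alternative 70%, success at 24 or more. The exact binomial calculation gives power 0.9586 (stated: about 96%) and one-sided alpha 0.0126; a cut-off of 23 would give alpha 0.0270. The figure reproduces but has no bearing on duration.

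**Inputs.**
- HPLC samples at Months 1, 2, 3, 4.5 and 6, then every 3 months to Month 24 (SAP 4.4.2.2).
- Target days 60, 90, 135, 180, 270 and so on to 720; windows ±7 days at Month 2 and ±30 days at Month 24 (Protocol Table 4).
- t0 is the first sample for which "there is no pRBC transfusion in the previous 60 days".
- One month is 30.4375 days (SAP 3.2).

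The Month 1 sample is in practice too early to be t0, because transfusion continues until conditioning, which starts on Day -6.

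**Value recorded for an ongoing responder** = (day of last HPLC sample − t0) / 30.4375.

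| t0 | Last sample Day 720 | Months |
|---|---|---|
| Day 60 | 660 / 30.4375 | 21.7 |
| Day 90 | 630 / 30.4375 | 20.7 |
| Day 135 | 585 / 30.4375 | 19.2 |
| Day 180 | 540 / 30.4375 | 17.7 |
| Day 270 | 450 / 30.4375 | 14.8 |
| Day 360 | 360 / 30.4375 | 11.8 |

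With visit windows the ceiling is (750 − 53) / 30.4375 = 22.9 months.

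**Effect of the data cut, no response ever lost.** With t0 equally likely at Days 60, 90, 135 and 180:
- Day 720: (21.7 + 20.7 + 19.2 + 17.7) / 4 = 19.8 months.
- Day 540: (15.8 + 14.8 + 13.3 + 11.8) / 4 = 13.9 months.

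**Three histories, one value.** Each of these is recorded as 360 / 30.4375 = 11.8 months: t0 at Day 360 and still responding at Day 720; t0 at Day 90 and withdrawn while responding at Day 450; t0 at Day 90 with the criteria met at Day 450 and failed at Day 540. Only the third is a completed duration.

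**Illustration with loss.** The documents give no loss rate, so these rates and the t0 distribution are assumptions. The simulation used 100,000 subjects, the scheduled visits, the same four t0 days and exponential loss from t0, and kept those with at least about 6 months in response.

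| Assumed annual loss | Uncensored mean | Uncensored median | Still responding at Day 720 | Kaplan-Meier median |
|---|---|---|---|---|
| 0% | 19.8 | 20.7 | 100% | not reached |
| 5% | 19.4 | 19.2 | 94% | not reached |
| 10% | 18.9 | 19.2 | 89% | not reached |
| 20% | 18.0 | 19.2 | 78% | not reached |
| 40% | 16.0 | 17.7 | 57% | not reached |

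The uncensored median can take only values on the visit grid (at 0% loss the middle falls between 19.2 and 20.7), so it is unchanged from 5% to 20% loss. The mean moves by 1.4 months over that range, while the proportion still responding falls by 16 percentage points.

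**The case against.** The best defence is that duration will not be read alone. SAP 4.4.3.1 also reports the proportion of responders who keep the response to Month 24, with an exact confidence interval, and a supplementary version for unrelated death or discontinuation. SAP 4.4 promises listings for all efficacy endpoints. Durability beyond Month 24 belongs to the separate long-term follow-up protocol. With complete follow-up, the uncensored mean is also a legitimate restricted mean time in response. The endpoint has no hypothesis and no success criterion.

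Much of this stands and limits the severity. It does not remove the problem: the main proportion counts dropouts as failures, the supplementary one drops those unrelated to drug product, and neither uses the time they contributed. The restricted-mean reading needs a common window, but t0 varies by subject and the SAP does not label the result that way.

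Three stronger readings are tempting and not supported:
- A reader might infer that every response is treated as ending at the last sample. A response lost before Month 24 ends at its last qualifying assessment, a real end limited by visit spacing.
- A reader might infer that results would look the same whether nobody or everybody lost response at Month 24. If all failed at the Month 24 sample, each duration would stop at Month 21, about 90 / 30.4375 = 3.0 months shorter, and the maintenance proportion would go from 100% to 0%. Loss after that sample is invisible to any method using this study's data.
- A reader might set the planned mean against a much longer true median. These are different quantities, Kaplan-Meier could not estimate such a median from this follow-up either, and loss in roughly the first 6 months is excluded by the definition of a responder.

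**Conclusion.** The concern holds for subjects still responding at their last HPLC sample. For them the recorded duration is right-censored and equals follow-up from t0: 17.7 to 21.7 months at Day 720 for t0 between Day 180 and Day 60, and no more than about 22.9 months with visit windows. The planned mean and median will therefore mainly describe t0 and length of follow-up, more so the more durable the responses are. The ceiling and the data-cut comparison rest on the scheduled visits and, for the averages, on four equally likely t0 days; the loss-rate table is illustrative only.

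The consequence is limited to the interpretation of one additional secondary, descriptive endpoint. The primary and key secondary tests are unaffected. The SAP should still be changed, because following it as written gives a figure that is easily misread as durability, and a better analysis is available from the same data.

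**What to change.** In SAP 4.4.3.1, analyse duration by Kaplan-Meier from t0 among Group C responders.

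- **Event:** the first HPLC assessment at which the weighted-average criteria, computed from t0 as in that section, are no longer met. This dates loss at the first failing sample, not the last qualifying one, a shift of about 3 months with quarterly visits. Say so.
- **Transfusion:** state how a pRBC transfusion after t0 is treated.
- **Censoring:** at the last HPLC assessment if still responding, including at Month 24, at an interim cut-off, and at withdrawal or death unrelated to drug product.
- **Drug-product-related death or discontinuation:** count as loss of response, in line with the existing supplementary rule for the Month 24 proportion.
- **Report:** the number with ongoing response, numbers at risk, and retention at 12 and 18 months from t0. Note that about the first 6 months are event-free by definition of the population. With a last sample at Day 720, only subjects with t0 by about Day 172 (720 − 18 × 30.4375) are observed for the full 18 months.
- **Label:** keep the descriptive summary, but call it observed time in response.

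The cost is a few lines of SAP text and one further analysis, with no new data. The drawback is that the median will probably be not reached. One limit remains: an average accumulated from t0 reacts slowly. For example, an HbA^T87Q percentage of 45% from Day 90 to Day 360 and 20% from Day 450 still averages (270 × 45 + 90 × 32.5 + 270 × 20) / 630 = 32.5% at Day 720. That follows from the response definition, and censoring does not change it.
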